Methodology: Strategy: 
 
Evaluate ocular and systemic safety profile of CBT-001 ophthalmic solution in patients with primary or recurrent pterygium, that are associated with moderate to severe pterygium vascularity;
 
Establish whether CBT-001 is efficacious in reducing pterygium vascularity;
 
Assess whether CBT-001 is efficacious in inhibiting pterygium lesion growth;
 
 Plan: A multicenter, double-masked, vehicle-controlled and parallel study is designed with 28 days TID repeat ocular dosing of vehicle and the highest tolerable dose (e.g., 0.2%), followed by 5-month post dose observation. Ophthalmic and physical examinations will be performed at screening, Day 1 and weeks 2, 4, 8, 16, and 24. External photograph of the pterygium eye will be taken using a digital camera and the lesion length, width and area as well as pterygium vascularity will be measured or graded from these images at an independent image reading center.	
Number of Subjects: 50 patients with primary or recurrent pterygium.	
Diagnosis and Main Criteria for Eligibility: Major Inclusion Criteria 
 
Primary pterygium with 0.6-3.5 mm lesion length from the anterior edge of limbus to the central cornea, associated with pterygium vascularity <math>\geq</math> Grade 3 using the 5-point Pterygium Hyperemia Grading Scale
 
	

- a. A minimum of Grade 3 (moderate) pterygium vascularity in the study eye at the screening (day -60 to day -7) and baseline (day 1) visits, using the 5-point Pterygium Hyperemia Grading Scale (0 = absent, 1 = trace, 2 = mild, 3 = moderate, 4 = severe);
- b. About 0.6-3.5 mm of encroachment of the pterygium onto the cornea of the study eye at the screening (day -60 to day -7) and baseline (day 1) visits as measured by slit lamp examination (investigator assessment). The measurement is as described by Welch et al [Welch et al, 2011]. A standard magnification of 16 is used and the variable aperture is focused on the pterygium from the limbus to the apex. Reading the size on the slit lamp scale, measurements are taken from the limbus to the apex of the lesion on the cornea and recorded to the nearest tenth of a millimeter.

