**Secondary Efficacy Endpoints:**

Comparison between drug-treated and vehicle-treated groups on change from baseline (Day 1) at Weeks 2, 4, 8, 16 and 24 in:

- Corneal lesion length, defined from the anterior edge of the limbus onto the central cornea
- Corneal lesion area;
- Corneal lesion width;

Comparison between drug-treated and vehicle-treated groups on changes of the severity grade of pterygium vascularity from baseline (Day 1) at Weeks 2, 8, 16 and 24;

Changes from baseline (Day 1) at Weeks 2, 4, 8, 16, and 24 in:

- Corneal lesion length
- Corneal lesion area
- Corneal lesion width

Change in severity grade of pterygium vascularity from baseline (Day 1) at Weeks 2, 4, 8, 16, and 24

Comparison between drug-treated and vehicle-treated groups on change from baseline (Day 1) at Weeks 2, 4, 8, 16 and 24 in:

- Topographic astigmatism in diopters

Comparison between drug-treated and vehicle-treated groups on change from baseline (Day 1) at Weeks 2, 4, 8, 16 and 24 in:

Scores of Pterygium Symptom and Life Quality (PSLQ) questionnaire

**Statistical Methods:** Two database locks are planned for the study, interim and final. The interim analysis will be performed after at least 80% of patients have completed their week 4 visit or discontinued prematurely. The final analysis will be performed after study completion.

The O'Brien-Fleming group-sequential method will be used for a multiple-comparison adjustment of p-values for efficacy due to analyzing the data for both interim and final analyses. For the final analysis, a 2-sided test with p-value  $\leq 0.048$  will be considered statistically significant for all between and within treatment comparisons.

- In general, continuous data will be summarized with descriptive statistics (number of patients, mean, standard deviation, median, minimum and maximum) and will be analyzed using analysis of variance (ANOVA) techniques or 2-sample t-tests for between-group comparisons, and paired t-tests for within-group analyses. Categorical variables will be summarized by sample size (N), frequency count and percent, and analyzed using Pearson's chi-square test or Fisher's exact test. Ordinal variables will be analyzed using the Cochran-Mantel-Haenszel (CMH) or the Wilcoxon rank-sum test for between-treatment comparisons and the sign-rank test for within-treatment comparisons. No imputation for missing data will be performed.

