**Duration of Study Follow-Up:** 1, 3, and 5 months after the completion of 28 days of continuous ocular dosing.

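### Name one repeated-measures model for each continuous secondary endpoint, so that a patient who misses a late visit still contributes (minor improvement)

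*Combined protocol and SAP*

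**What the plan says.** The Statistical Methods paragraph of the synopsis says that continuous data "will be analyzed using analysis of variance (ANOVA) techniques or 2-sample t-tests for between-group comparisons, and paired t-tests for within-group analyses". It closes with "No imputation for missing data will be performed". At the final analysis, a two-sided p-value of at most 0.048 "will be considered statistically significant for all between and within treatment comparisons".

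The Secondary Efficacy Endpoints list asks for both kinds of test:
- Between arms: "Comparison between drug-treated and vehicle-treated groups on change from baseline (Day 1) at Weeks 2, 4, 8, 16 and 24 in" lesion length, area and width, and in the same form for topographic astigmatism and the PSLQ score.
- Within arm, as endpoints in their own right: "Changes from baseline (Day 1) at Weeks 2, 4, 8, 16, and 24 in" the same three lesion measures.

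The Schedule of Events plans photography on Day 1 and at all five later visits. Its footnote b says that efficacy is read from those photographs at an outside reading centre. Three of the five visits fall after dosing has stopped, "1, 3, and 5 months after the completion of 28 days of continuous ocular dosing".

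The plan names no repeated-measures model and no missing-data sensitivity analysis, and it does not define ANOVA techniques further. It gives no dropout rate, SD, between-visit correlation or allocation ratio.

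**The concern.** A paired t-test needs both the Day 1 value and the value at the visit. Without imputation, a patient absent at Week 24 is therefore excluded from that test, and the Week 2 to Week 16 measurements already on file are not used. The two-sample t-test behaves in the same way.

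If absence has nothing to do with the lesion, the cost is precision, in both kinds of test. If patients whose lesions grow are more likely to leave, those who stay look better than the group that was randomised. Under one common rule in both arms, this error largely cancels between arms when the drug does nothing, and dilutes the contrast when it works. Within an arm nothing cancels it, so a zero change can look like shrinkage.

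This bears on one stated aim: "Assess whether CBT-001 is efficacious in inhibiting pterygium lesion growth". Late lesion change speaks to that aim, and the late visits in the off-treatment months are where loss is most plausible.

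**Working it through.** **Plan's own figure.** The only reproducible number involved is the final level. A two-look O'Brien-Fleming boundary with equally spaced looks and overall two-sided 0.05 gives a final critical value of 1.977 and p = 0.0480, matching the plan. It serves here only as the test level.

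**Inputs.** From the documents: 50 patients, five post-baseline visits, level 0.048. Assumed: 25 per arm, SD of change 0.4 mm, constant between-visit correlation 0.7, and loss before Weeks 8, 16 and 24. All results are at Week 24.

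**1. Random loss.** A patient with Weeks 2 and 4 on file has a Week 24 value predicted with R² = 2 × 0.7² / (1 + 0.7) = 0.576. The effective number per arm follows from 1/n_eff = (1 − R²)/n_obs + R²/n.
- 22% missing: n_obs = 19.5; 1/n_eff = 0.424/19.5 + 0.576/25 = 0.0448; n_eff = 22.3. The standard error falls by 1 − √(19.5/22.3) ≈ 6% to 7%.
- 35% missing: n_obs = 16.25; 1/n_eff = 0.424/16.25 + 0.576/25 = 0.0491; n_eff = 20.4. The fall is about 11%.

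Simulation gives 0.125 to 0.118 mm (6%) and 0.141 to 0.129 mm (9%). Neither analysis is biased. With R² = 0.49 (one earlier value), 20% loss and an effect set for 80% power on full data, between-arm power goes from 70.7% to 75.1%. The within-arm gain is about the same.

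**2. Growth-driven leaving, same rule in both arms.** At each late visit, the log-odds of leaving rise by 1 or 2 per 0.4 mm of last measured growth. Observed-case t-tests are compared with a REML mixed model (unstructured covariance, Kenward-Roger).

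*Between arms.* With no true effect, rejection is 4% to 6%, so there is no inflation. With about 25% missing in the arm that has no change, a true 0.30 mm reads 0.27 to 0.29 mm if the difference builds up over the visits, and 0.24 to 0.27 mm if it is present at every visit. The model gives 0.30. The dilution is therefore 3% to 20%.

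*Within the drug arm, true change 0.*

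| Slope | Missing | Observed-case mean (mm) | Rejection | Model mean (mm) | Model rejection |
|---|---|---|---|---|---|
| 1 | 23% | −0.062 | 9.7% | −0.002 | 5.2% |
| 2 | 25% | −0.098 | 19.4% | 0.000 | 5.0% |
| 2 | 38% | −0.149 | 33.6% | −0.002 | 7.6% |

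Hand check of the second row: 25% missing leaves 18.75 patients, so the standard error is 0.4/√18.75 = 0.092 mm. The bias is 0.098/0.092 = 1.06 standard errors, and P(Z > 1.977 − 1.06) is about 0.18, in line with 19.4%.

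**3. Looser link to the measurement.** If leaving follows what the patient perceives, and that correlates 0.5 with measured change, the within-arm shrinkage at 25% missing starts at about 0.03 mm and rejection is about 5.5% to 8%. At 38% missing it is about 7% to 10%.

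**4. Other ranges.** For slope 2 at about 25% missing, correlation 0.5 to 0.9 gives 0.08 to 0.12 mm (13% to 28% rejection). SD 0.2 to 0.8 mm scales the bias from 0.05 to 0.20 mm with rejection unchanged. At 8% to 13% missing, within-arm shrinkage is 0.03 to 0.06 mm with 5% to 10% rejection, and about 5% under the looser link.

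**5. Leaving driven by unseen growth.** With slopes 2 (drug) and 1 (vehicle), the within-arm bias drops from −0.170 to −0.053 mm, so about 31% remains. The model corrects this only in part.

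Monte Carlo error is about 0.003 mm and 0.5 to 1.1 points.

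**The case against.** **The leaving rule behind the larger figures fits the documents loosely.** The site assesses lesion size only at screening and Day 1. After that the reading centre measures the photographs, and nothing says its values return to sites or patients. Slope 2 is also steep: the odds of leaving rise e² = 7.4-fold per 0.4 mm at each of three visits. This stands. The 19% and 34% rejection rates are near a worst case.

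**The quoted sentence is not an error.** A mixed model needs no imputation, ANOVA techniques could cover repeated measures, and this is a short-form protocol. This stands too, and makes the point an improvement in specification. But no such model is named, and the paired t-test leaves no room for one.

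**Within-arm change is weak evidence in a vehicle-controlled trial.** True, and a mixed model does not turn it into evidence of drug effect. The plan nevertheless lists these changes as secondary endpoints and tests them.

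**Stronger readings that a reader might infer:**
- *The late between-arm comparisons will produce false benefit.* This needs growth to drive leaving more strongly in the drug arm (slopes 1 against 0.5, or 2 against 1: 0.03 to 0.07 mm, 6% to 8% rejection). The Plan paragraph says "A multicenter, double-masked, vehicle-controlled and parallel study is designed", and the documents give no reason to expect such a difference.
- *The within-arm tests are the main thing protected.* That holds only for false positives under a shared rule. The precision gain is about equal for both kinds of test, and the between-arm estimate also escapes dilution.
- *The primary is compromised.* It is an ordinal grade at Week 4, at the end of dosing, much less exposed and outside this model.

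**Conclusion.** The point holds as a minor, low-severity improvement. Single-visit tests without imputation discard information that the trial will already have, and a repeated-measures model would recover it for both between-arm and within-arm results.

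The true size is unknown, because dropout, SD, correlation and allocation are all assumed. On those assumptions, the gain in between-arm standard error is 6% to 11% under random loss. The larger distortions need leaving tied to lesion growth at about 25% missing or more. The highest within-arm rejection rates also need that tie to be to the measured value itself. If only about 10% of patients miss Week 24, little changes. The model's near-zero bias rests on leaving that depends on values already observed.

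**What to change.** For lesion length, area, width, topographic astigmatism and PSLQ score (if treated as continuous), name one mixed model for repeated measures per endpoint as the main analysis. Terms: treatment, visit, treatment by visit, Day 1 value and Day 1 value by visit. Use unstructured covariance and Kenward-Roger degrees of freedom, and pre-specify a fallback covariance in case of non-convergence. Read each visit's between-arm contrast and within-arm change from this model. Keep the planned single-visit tests as supportive. Tabulate missing visits by arm and visit, including for late vascularity, which is ordinal and not covered by the model. Leave the Week 4 vascularity primary as it is.

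Optional: a simple delta-adjusted sensitivity analysis for Weeks 8 to 24, since the model only partly corrects leaving driven by unseen values. Shifting the drug arm's missing values by delta moves the contrast by delta times that arm's missing share; at 20% missing, 0.1 to 0.4 mm moves it 0.02 to 0.08 mm. If it is added, the no-imputation sentence needs an exception for it.

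Cost: analysis-plan wording and modest programming, with no new visits or data. Two downsides remain. Convergence with 50 patients is not assured: the simulated fits all converged, but most started from the true covariance. The model's within-arm test can also reject slightly too often (7.6% at 38% missing).

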## ATTACHMENT: SCHEDULE OF EVENTS

Study Procedures	Screening Days -60 to -7	Day 1 a	Week 2 (± 5 days)	Week 4 (± 5 days)	Week 8 (± 7 days)	Week 16 (± 7 days)	Week 24 (± 7 days)
Informed Consent/Authorization	X						
Inclusion/Exclusion Criteria	X	X					
Demographics	X						
Medical / Ocular History	X						
Pregnancy Test	X	X	X				
Serious Medical Events (SME)	X	X					
Subject ID Assignment	X						
Concomitant Medications/Concurrent Procedures	X	X	X	X	X	X	X
Pterygium Symptom and Life Quality (PSLQ) questionnaire	X	X	X	X	X	X	X
Vital Sign measurements (blood pressure, heart rate, body temperature)	X	X	X	X	X	X	X
Hematology & Blood Chemistry	X			X			X
Pterygium Photography b		X	X	X	X	X	X
Pterygium Vascularity Assessment	X	X					
Pterygium Morphology Assessment	X	X					
Pterygium Size Assessment	X	X					
Biomicroscopy	X	X	X	X	X	X	X
Topographic Astigmatism	X	X	X	X	X	X	X
Best-Corrected Visual Acuity	X	X	X	X	X	X	X
Intraocular Pressure	X	X	X	X	X	X	X
Ophthalmoscopy (dilated)	X	X		X			X
Adverse Events		X	X	X	X	X	X
Randomization		X					
Study Medication		Dispense	Collect	Collect	Collect		
Exit							X

a All measurements at baseline Day 1 are prior to the instillation of first dose

b Efficacy endpoints will be assessed using pterygium photography at an independent image reading center

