#### Major Exclusion Criteria

- Uncontrolled systemic disease
- Active ocular disease, corneal abnormalities other than pterygium, active ocular infection, or any ocular pathology unrelated to pterygium in either eye that could affect the assessment of the pterygium
- History of ocular herpes disease in either eye
- Any retina disease that could affect visual acuity (e.g., age-related macular degeneration)
- Any ocular surgical procedure within the last 3 months
- Anticipated wearing of contact lenses during any portion of the study. Patients, who wear soft contact lenses should discontinue wearing them at least 3 days prior to Day 1 visit. Patients wearing rigid gas permeable or hard contact lenses should discontinue wearing them at least 3 weeks prior to Day 1 visit
- Female patients who are pregnant, nursing, or planning a pregnancy during the study
- Current enrollment in an investigational drug or device study or participation in such a study within 30 days prior to entry into this study
- History of myocardial infarction or stroke
- Any condition or situation which, in the investigator's opinion, may put the patient at significant risk, may confound the study results, or may interfere significantly with the patient's participation in the study
- Known allergy or sensitivity to the study medication(s) or its components

- Double pterygium (i.e., eye with nasal and temporal pterygia)
- Pterygium that would require surgery
- Pingueculae, pseudo-ptyerygia (e.g., chemical or thermal burn, trauma, marginal corneal disease); neoplasia (e.g., carcinoma in situ, squamous cell carcinoma, other neoplastic diseases)
- Current or anticipated use of topical ophthalmic medications in the study eye. Patients must have discontinued use of ophthalmic medications in the study eye for at least 2 weeks prior to Day 1 visit.
- **Eye:** an eye does not qualify for the study if any of these criteria are present. However, if none of these criteria are present in the other eye, the patient may still qualify for enrollment based on that eye provided the patient/eye meets all the inclusion and none of the exclusion criteria.

**Test Product, Dose and Mode of Administration, Batch Number:** CBT-001 ophthalmic solution of vehicle or the highest tolerable dose (e.g., 0.2%), unilateral topical ocular dosing

**Duration of Treatment:** 28 days of continuous unilateral ocular dosing with follow-up period of 1, 3, and 5-month post dose

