**Efficacy:**

**Primary Efficacy Endpoint:**

Comparison between drug-treated and vehicle-treated groups on changes of the severity grade of pterygium vascularity from baseline (Day 1) at Week 4;

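### Does leaving the Week 4 photograph unordered against dilating drops and the last study drop undermine the primary redness comparison?

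*Combined protocol and SAP*

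**What the plan says.** Under Primary Efficacy Endpoint, the comparison between arms is on "changes of the severity grade of pterygium vascularity from baseline (Day 1) at Week 4". Footnote b of the Schedule of Events gives the source of the grade: "Efficacy endpoints will be assessed using pterygium photography at an independent image reading center".

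Three provisions bear on drops in the eye:

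- Footnote a: "All measurements at baseline Day 1 are prior to the instillation of first dose".
- Major Exclusion Criteria: an eye is excluded for "Current or anticipated use of topical ophthalmic medications in the study eye", and "Patients must have discontinued use of ophthalmic medications in the study eye for at least 2 weeks prior to Day 1 visit".
- The Methodology plan sets "28 days TID repeat ocular dosing of vehicle and the highest tolerable dose", so patients are still dosing, or have just stopped, when the Week 4 photograph is taken (window ± 5 days).

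The Schedule of Events marks photography at Day 1 and Weeks 2, 4, 8, 16 and 24. It marks dilated ophthalmoscopy at Screening, Day 1, Week 4 and Week 24. No text orders procedures within a visit or sets an interval between the last study drop and a photograph.

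**The concern.** The outcome is how red the eye looks in a photograph, so anything recently put in the eye could matter. The plan seems to recognise this before baseline, with a two-week washout and a pre-dose rule, and then to say nothing about the other half of the same change score. A site could dilate first at Week 4, photograph afterwards, and still comply. If the drop reddened or blanched the conjunctiva, the grade would pick up noise, or part of a real drug–vehicle difference would be hidden. Weeks 2, 8 and 16 have no dilation, so the course over time could also mix examination conditions. Separately, on three-times-daily dosing the photograph might follow a study drop by minutes or by many hours, and a brief effect of the active drop could be read as a lasting one. With 50 patients there is little room for lost precision.

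**Working it through.** **1. Conditions at each photograph visit (Schedule of Events)**

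| Visit | Photograph | Dilation | Study drops |
|---|---|---|---|
| Day 1 | yes | yes | not yet started |
| Week 2 | yes | no | dosing |
| Week 4 | yes | yes | end of dosing |
| Week 8 | yes | no | stopped |
| Week 16 | yes | no | stopped |
| Week 24 | yes | yes | stopped |

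The two visits in the primary endpoint carry the same dilated examination, unordered at both. The washout covers the patient's own medications, not drops used in clinic. Neither provision makes Day 1 free of diagnostic drops, so for dilation the two ends of the change score stand on the same footing.

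**2. Effect of dilation order on the change score**

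Let D = 1 if a photograph follows the dilating drop, and let s be the resulting shift in grade. Then

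observed change = true change + s × (D at Week 4 − D at Day 1).

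Assumed inputs, none of them in the documents: 25 per arm, SD of change 0.6–0.9 grade, share p of photographs after the drop 20–50%, s of 0.5 or 1 grade, and a standardised effect of 0.814, which gives 80% power by a two-sample t-test at the plan's two-sided 0.048. Power is recomputed at 0.814 / √(1 + proportional rise in variance).

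- *Same order at both visits.* The bracket is zero, no variance is added, and power stays at 80%.
- *Shift at Week 4 only.* Added variance is p(1 − p)s². For s = 0.5 the rise runs from 0.2 × 0.8 × 0.25 / 0.81 = 4.9% to 0.5 × 0.5 × 0.25 / 0.36 = 17.4%, and power is 73–78%. For s = 1 the rise is 20–69% and power is 57–73%.
- *Order varying independently at both visits.* Added variance is 2p(1 − p)s². For s = 0.5 the rise is 0.08 / 0.81 = 9.9% to 0.125 / 0.36 = 34.7%, and power is 67–76%. For s = 1 it is 0.32 / 0.81 = 39.5% to 0.5 / 0.36 = 138.9%, and power is 44–66%.

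The second case needs a clean baseline, which the plan does not require. The third needs order to vary at random from visit to visit. The first is what a site with a fixed routine produces.

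In all three cases D is unrelated to arm under masking and randomisation. If the drug does nothing, both arms have the same distribution of grades and the 0.048 level is kept. The possible cost is power, not bias in favour of the drug.

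**3. Blanching that hides a difference**

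If a drop halves the visible difference in 30% or 50% of photographs, the effect becomes 0.85 or 0.75 of its size (1 − 0.3 × 0.5; 1 − 0.5 × 0.5). Standardised effects are 0.814 × 0.85 = 0.692 and 0.814 × 0.75 = 0.611, with power 66% and 55%. A consistent order does not cancel this, but it works against the drug, and both the halving and the shares are assumed.

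**4. Time since the last study drop**

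Taking Week 4 as Day 28, the window is Day 23 to Day 33. An acute effect of the active ingredient could differ by arm. A 0.25-grade short-lived shift in the active arm alone would reach significance about 16–30% of the time (SD 0.9 down to 0.6). That would still be a real drug–vehicle difference near the end of dosing. The open question is whether it lasts, and the plan collects data on that: vascularity is compared again at Weeks 8, 16 and 24. The earliest Week 8 photograph is Day 56 − 7 = 49, which is 49 − 28 = 21 days after scheduled dosing ends.

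**The case for a change.** The strongest case for acting is that the gap is real, lies on the primary endpoint and is cheap to close. No text orders the photograph at any visit, nothing obliges a site to keep one order, and unrecorded drop times cannot be recovered later. Randomisation and central reading do not fix the interval since the last study drop, which is the one element that could differ by arm. Cancellation of a dilation shift also assumes the shift is additive. On a 0–4 scale with entry at grade 3 or above, a reddening shift can meet the ceiling.

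All of that stands as description. What does not stand is the step to a flaw that needs amending. The power losses come wholly from assumed agents, shares and shifts, and with no shift there is no loss. They also use a t-test, whereas Statistical Methods assigns ordinal variables to Cochran–Mantel–Haenszel or Wilcoxon tests. The conditions are not uncontrolled either: the study is double-masked and vehicle-controlled, grades are read independently, other topical ophthalmic medication is excluded, and concomitant medication is recorded at every visit. Differences in dilation between visits leave the between-arm comparison at each visit intact, since both arms follow one schedule; at most they touch the secondary within-group changes. Adjusting for time since the last drop would not improve the primary result: the interval arises after randomisation, may depend on tolerability or adherence, and does not fit the rank-based analysis.

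**Conclusion.** The Schedule of Events leaves the order of photography and diagnostic drops unwritten at every photograph visit, Day 1 included, and does not time photographs against the last study drop. No stated rule produces a wrong result. Dilation accompanies both visits in the primary endpoint, is unrelated to arm, and drops out of the change score where a site keeps its routine and the shift is additive. Its cost cannot be estimated from the documents: it may be nothing, and the reductions in power shown above hold only under assumed shifts. An acute study-drop effect could differ by arm, but the documents give no evidence of one, and the off-treatment visits would help show whether any Week 4 difference lasts.

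The document is titled Protocol-short, and order within a visit is ordinary content for a full protocol or photography manual. The table already lists photography above intraocular pressure and dilated ophthalmoscopy; that is not a stated sequence, but nothing points the other way. This is a gap that sites would be expected to fill sensibly. The conclusion assumes reasonably consistent site routine and no large acute drop effect. The plan can stand.
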